1.2 Name and Description of Investigational Product or Intervention

Study intervention: Oral furosemide

The information provided in this section was obtained from Food and Drug Administration (FDA) package insert.¹⁹ Furosemide (Lasix[®]) is a diuretic which is an anthranilic acid derivative. Tablets contain furosemide (active ingredient) and lactose monohydrate NF, magnesium stearate NF, starch NF, talc USP, and colloidal silicon dioxide SF (inactive ingredients). Chemically, it is a 4-chloro-N-furfuryI-5-sulfamoylanthranilic acid. It is available in 20, 40 and 80 mg tablets.

Furosemide is a white to off-white odorless crystalline power. It is practically insoluble in water, sparingly soluble in alcohol, freely soluble in dilute alkali solutions and insoluble in dilute acids.

Mechanism of action: Furosemide inhibits the absorption of sodium and chloride not only in the proximal and distal tubules but also in the loop of Henle. The action on the distal tubule is independent of any inhibitory effect on carbonic anhydrase and aldosterone.

Pharmacokinetics: The onset of diuresis following oral administration is within 1 hour. The peak effect occurs within the first or second hour. The duration of diuretic effect is 6 to 8 hours. In fasted normal men, the mean bioavailability of oral furosemide tablets is 64% of that from an intravenous injection of the drug. The terminal half-life of furosemide is approximately 2 hours. Peak plasma concentrations increase with increasing dose, but times-to-peak do not differ among doses. Furosemide is predominantly excreted unchanged in the urine.

Indications and usage: Furosemide is indicated in adults and pediatric patients for the treatment of edema associated with congestive heart failure, cirrhosis of the liver, and kidney disease. Oral furosemide may also be used in adults for the treatment of hypertension alone or in combination with other antihypertensive agents.

Contraindications: Furosemide is contraindicated in patients with anuria and in patients with a history of hypersensitivity to furosemide.

Dosing and dose changes with rationale

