During the 6-week dose escalation period (period 1), participants who are not taking oral furosemide at study entry will take 80 mg oral furosemide twice a day for 14 days and then, if the dose was tolerated, they will take 120 mg oral furosemide twice a day for 14 days and then, if the dose was tolerated, they will take 160 mg oral furosemide twice a day for 14 days. If a patient is taking oral furosemide at study entry, the participant will remain on his/her prescribed oral furosemide dose for the first 2 weeks of the dose escalation period. If a participant is taking another loop diuretic (e.g. bumetanide), we will calculate the corresponding oral furosemide dose (i.e. 1 mg bumetanide = 40 mg furosemide). The participant will discontinue the other loop diuretic and receive the equivalent dose of oral furosemide for the first 2 weeks of the dose escalation period. The first dose will then be increased by 50%, rounded to the nearest whole tablet strength of existing (i.e. available) furosemide tablet formulations (not to exceed 320 mg/day) at week 2 and, if tolerated, the second dose will be increased by 50% at week 4, rounded to the nearest whole tablet strength of existing (i.e. available) furosemide tablet formulations (not to exceed 320 mg/day). Establishing ceiling dose thresholds by increasing the prior dose by 30-50% is the recommended approach in heart failure patients per the American College of Cardiology Foundation/American Heart Association task force on practice guidelines.²⁰ The maximum proposed study dose is 160 mg twice daily (320 mg total per day), which is well below the maximum oral furosemide daily dose of 600 mg/day listed in the furosemide package insert.¹⁹ In addition, the planned furosemide doses are consistent with available formulations (i.e. study doses can be provided using currently marketed furosemide tablet strengths) and standard clinically utilized/approved doses for the FDA-labeled indications. We are not testing higher doses due to the potential increased risk of AEs necessitating drug discontinuation.

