2.1 Primary Objectives

Period 1 (dose escalation = short-term outcomes; 6-weeks) and Period 2 (follow-up = longer-term outcomes; 12-weeks)

Short-term and longer-term efficacy: To test the hypothesis that furosemide will increase 24-hour urine volume at its maximally tolerated dose in individuals with HD-dependent ESKD. 24-hour urine volumes will be used as the primary endpoint for both short-term and longer-term efficacy assessments.

Short-term and longer-term safety: To evaluate the short-term (6-weeks) and longer-term (12-weeks) safety of escalating doses of furosemide in individuals with HD-dependent ESKD. Safety outcomes will include the following:

- Serum potassium level <3.2 mEq/L
- Serum magnesium level <0.8 mg/dL
- Serum corrected calcium level <7 mg/dL
- Serum furosemide level >12 microgram/L
- Serious dialysis-associated hypotension defined as hypotension requiring hospitalization or treatment in an emergency room and not attributable to overt sepsis, acute myocardial infarction, or other cardiovascular event (e.g. aortic dissection)
- Severe or very severe rash, tinnitus, or hearing change not attributable to causes other than furosemide
- Inner EAR score decrease by ≥10 points

Short-term and longer-term tolerability: To evaluate the short-term and longer-term tolerability of furosemide in individuals with HD-dependent ESKD. Tolerability will be assessed by:

• Severe or very severe cramping, dizziness/pre-syncope, unusual tiredness/weakness, chest pain, nausea, vomiting, or diarrhea not attributable to causes other than furosemide

Short-term and longer-term acceptability: To evaluate the short-term and longer-term acceptability of furosemide in individuals with HD-dependent ESKD. Acceptability will be assessed by:

- Participant affirmative response to question: "If recommended, would you be willing to stay on the dose of furosemide you have received during the last week?"
- Recruitment rates
- Drop-out rates

Short-term adherence: To evaluate short-term and longer-term adherence to furosemide among individuals with HDdependent ESKD. Adherence will be assessed by:

- Pill counts
- Serum and urine furosemide levels

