6.1 Primary Endpoints

Short-term and longer-term efficacy- urine volume (assessed separately)

- Among participants with baseline 24-hour urine volume ≥200 mL: incidence of ≥25% increase in urine volume
- Among participants with baseline 24-hour urine volume <200 mL: incidence of a ≥50 mL increase in urine volume to a urine volume of at least 100 mL/24-hours

Short-term and longer-term safety- electrolytes (assessed separately)

- Incidence of serum potassium <3.2 mEq/L
- Incidence of serum magnesium <0.8 mg/dL
- Incidence of serum corrected calcium <7.0 mg/dL

Short-term and longer-term safety- furosemide levels

• Incidence of serum furosemide level >12 microgram/L

Short-term and longer-term safety- BP

 Incidence of dialysis-associated hypotension requiring hospitalization or treatment in an emergency room and not attributable to overt sepsis, acute myocardial infarction, or other cardiovascular event (e.g. aortic dissection)²¹

Short-term and longer-term safety- symptoms (assessed separately)

- Incidence of severe or very severe patient-reported rash, tinnitus, or hearing change) not attributable to causes
 other than furosemide
- Incidence of 10-point decrease in Inner EAR instrument score

Short-term and longer-term tolerability- symptoms (assessed separately)

• Incidence of severe or very severe patient-reported cramping, dizziness/pre-syncope, unusual tiredness/weakness, chest pain, nausea, vomiting, or diarrhea not attributable to causes other than furosemide

Short-term and longer-term acceptability

• Incidence of an affirmative response to the furosemide acceptance question

Short term- and longer-term adherence

• Incidence of participants having <20% of furosemide pills remaining at pill counts

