6.2 Exploratory Endpoints

Short-term and longer-term efficacy- alternative definitions (assessed separately)

- Absolute change in urine volume from baseline (continuous in mL urine)
- Percentage change in urine volume from baseline (continuous in %)

Short-term and longer-term safety- electrolytes- alternative definitions (assessed separately)

- Absolute change in serum potassium from baseline (continuous in mEq/L)
- Absolute change in serum magnesium from baseline (continuous in mg/dL)
- Absolute change in serum corrected calcium from baseline (continuous in mg/dL)
- Percentage change in serum potassium from baseline (continuous in %)
- Percentage change in serum magnesium from baseline (continuous in %)
- Percentage change in serum corrected calcium from baseline (continuous in %)

Short-term and longer-term safety- BP- alternative definitions (assessed separately)

- Incidence of intradialytic systolic BP <80 mmHg²¹
- Incidence of intradialytic systolic BP <90 mmHg⁴¹
- Lowest systolic BP during HD (continuous in mmHg)

Short-term and longer-term acceptability alternative definitions (assessed separately)

- Number (percentage) of participants withdrawing from the study
- Number (percentage) period 1 participants not continuing to period 2

Short-term and longer-term adherence alternative definitions (assessed separately)

- Number (percentage) of furosemide tablets not taken (# tablets remaining/# tablets provided)
- Serum furosemide level (continuous in microgram/L and binary, present vs. absent)
- Urine furosemide level (continuous in microgram/L and binary, present vs. absent)

Clinical endpoints (assessed separately)

- Change in 24-hour creatinine clearance from baseline (continuous in ml/min/1.73m²)
- Percentage change in 24-hour creatinine clearance from baseline (continuous in %)
- Change in 24-hour fractional excretion of sodium from baseline (continuous in %)

- Change in 24-hour fractional excretion of urea from baseline (continuous in %)
- Percentage change in 24-hour fractional excretion of urea from baseline (continuous in %)
- Pre-HD systolic BP (mmHg on a per-HD treatment basis)
- IDWG (kg on a per-HD treatment basis)
- UF volume (mL on a per-HD treatment basis)
- UF rate (mL/h/kg on a per-HD treatment basis)
- Target weight achievement (post-HD weight (kg) within 1kg of prescribed target weight) (binary on a per-HD treatment basis)

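### The primary safety cut-off for serum furosemide (12 microgram/L) has no stated source and lies far below the level expected soon after a study dose, so it mostly registers recent dosing

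*Combined protocol and SAP*

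**What the plan says.** Section 6.1 lists "Incidence of serum furosemide level >12 microgram/L" among the primary safety endpoints, short-term and longer-term. Section 2.1 has the same item, "Serum furosemide level >12 microgram/L", and the synopsis repeats it under safety evaluations. Value and unit agree in all three places. None of them gives a derivation, a reference or an assay limit.

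Section 1.2 supplies some kinetics: "the mean bioavailability of oral furosemide tablets is 64% of that from an intravenous injection of the drug" (in fasted normal men), "The terminal half-life of furosemide is approximately 2 hours", "The peak effect occurs within the first or second hour" and "Furosemide is predominantly excreted unchanged in the urine". It gives no distribution volume and no expected concentration. A participant not on furosemide at entry "will take 80 mg oral furosemide twice a day for 14 days", then moves to 120 mg and 160 mg twice daily if each step is tolerated. Participants already on a loop diuretic begin at their own or an equivalent dose.

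Blood is drawn at mid-week dialysis sessions (section 4.1), when the session starts (section 9.1, Retention). I found no instruction on the interval since the last tablet, and the measurements in section 5.1 do not include the time of the last dose.

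The same assay serves as an exploratory adherence measure in section 6.2: "Serum furosemide level (continuous in microgram/L and binary, present vs. absent". Section 6.3.4 analyses the level as a binary primary safety measure; section 6.3.5 also analyses it as a continuous exploratory one.

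**The concern.** A safety cut-off on drug level is useful if it separates excess exposure from ordinary exposure. Doses here are tens of milligrams or more, and the cut-off is 12 millionths of a gram per litre. If ordinary dosing puts participants well above it for many hours, crossing it says that a tablet was taken recently and says little about toxicity.

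The event rate would then reflect adherence and tablet timing. The binary analysis in section 6.3.4, which looks for dose-related differences, would partly measure how long each dose stays above a very low line. Readers of the pilot, and the designers of the later randomised trial it is meant to inform, could take a high rate as a safety signal when it is mainly a record of drug intake.

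**Working it through.** The plan shows no calculation behind the value 12, so there is no figure of its own to reproduce. The check asks what level a study dose would produce.

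**Inputs from the documents.** Bioavailability F = 0.64 and half-life 2 h (section 1.2); study doses 80 to 160 mg twice daily (sections 1.2 and 3.5.2); cut-off 12 microgram/L (section 6.1).

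**Assumptions not in the documents.** Distribution volume V of 10 to 100 L; a one-compartment model with instant absorption; a carried-in dose of 20 mg (the smallest listed tablet) as a low case.

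**Formulas.**
- Initial level: C0 = F × dose / V
- Level at time t: C(t) = C0 × 2^(−t / 2 h)
- Hours above the cut-off: 2 h × log2(C0 / 12)

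**Worked case, 80 mg.** The absorbed amount is 80 × 0.64 = 51.2 mg = 51,200 microgram. With V = 10 L, C0 = 5,120 microgram/L, and the time above 12 is 2 × log2(426.7) = 17.5 h. With V = 100 L, C0 = 512, and the time is 2 × log2(42.7) = 10.8 h.

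| Dose | V (assumed) | C0 (microgram/L) | C0 / 12 | Hours above 12 | Level at 12 h | Level at 16 h |
|---|---|---|---|---|---|---|
| 80 mg | 10 L | 5,120 | 427 | 17.5 | 80 | 20 |
| 80 mg | 100 L | 512 | 43 | 10.8 | 8 | 2 |
| 160 mg | 10 L | 10,240 | 853 | 19.5 | 160 | 40 |
| 160 mg | 100 L | 1,024 | 85 | 12.8 | 16 | 4 |
| 20 mg | 10 L | 1,280 | 107 | 13.5 | 20 | 5 |
| 20 mg | 100 L | 128 | 11 | 6.8 | 2 | 0.5 |

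**Volume needed to stay at or below 12.**
- At the initial level: 51,200 / 12 = 4,267 L for 80 mg; 102,400 / 12 = 8,533 L for 160 mg.
- At 12 h (six half-lives): 51,200 / (12 × 64) = 67 L for 80 mg; 133 L for 160 mg.
- At 16 h (eight half-lives): 51,200 / (12 × 256) = 17 L for 80 mg; 33 L for 160 mg.

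**Allowing for absorption.** With first-order absorption and the peak level placed at 1 to 2 h (the time of peak effect, used as a proxy), the peak after 80 mg is about 2,560 to 3,620 microgram/L at 10 L and 256 to 362 at 100 L. The lowest of these is still 256 / 12 = 21 times the cut-off.

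**Half-life.** Elimination is mainly renal, so 2 h may be too short for dialysis patients, but the documents give no other figure. If it were 4 h, the 16 h break-even volume for 80 mg would be 51,200 / (12 × 16) = 267 L.

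The level soon after a dose is thus far above 12 throughout the assumed range. The level at the blood draw can fall on either side, depending on timing, dose, volume and half-life.

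**The case against.** The strongest reply is that the trial does not measure the initial level. It measures the level at the start of a mid-week session, an unstated time after the last tablet, and twice daily does not guarantee a 12 h spacing. At 12 h after 80 mg the model gives 8 to 80 microgram/L over 100 to 10 L; at 16 h any volume above about 17 L puts the participant below the cut-off. This stands. A reader might infer that nearly every adherent participant will be flagged, or that incidence will approach 100%. The documents do not support that, because they fix neither the interval nor the volume. Repeated draws raise the chance of at least one crossing, but by an amount the documents do not allow one to estimate.

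It also stands that section 1.2 predicts no concentration without an assumed volume, and that its bioavailability figure comes from fasted normal men.

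A reader might also infer a thousand-fold unit slip. It is possible, but the documents give no toxic level, no source for 12 and no assay unit other than microgram/L, so it is not shown.

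The overlap with adherence is partial. The primary adherence endpoint is pill count (section 6.1); the present-or-absent level is exploratory and is not defined by the value 12. The continuous level is already planned (sections 6.2 and 6.3.5). Electrolytes, serious hypotension, symptoms and the hearing score are assessed separately, so a single uninformative endpoint does not misreport the drug's safety as a whole.

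The objection does not rescue the cut-off. If the result depends on when the tablet was taken, and that time is not recorded, the endpoint cannot be read as excess exposure.

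**Conclusion.** The point holds. The cut-off is unsupported in the documents and, for an 80 mg dose, is about 43 to 427 times below the initial level over an assumed 10 to 100 L. The direction does not hinge on that range: only a volume of about 4,267 L or more would bring the initial level down to 12. With a 2 h half-life the level stays above the cut-off for about 10.8 to 17.5 h.

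Followed as written, the endpoint counts recent dosing as a safety event. Participants sampled at about 16 h or later, or on a low carried-in dose, can fall below it for reasons unrelated to safety.

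The consequence is limited. The level is not among the events that end up-titration (sections 1.2, 1.3.1, 3.5.2 and 4.3) or the trial-defined adverse events (section 7.3.2). The harm is to interpretation of this one primary safety endpoint, not to dosing. The size rests on the assumed volume, the one-compartment model, and section 1.2's bioavailability and half-life applying to this population.

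**What to change.** 1. Check the value and unit against the source of the threshold and the units in which the laboratory reports the assay. State the source, and correct the synopsis, section 2.1 and section 6.1 together.
2. Record the time of the last furosemide dose at each blood draw, and interpret the already planned continuous level by time since dose.
3. Until the value and unit are confirmed, do not count a level above 12 microgram/L as a safety event.

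No replacement threshold is proposed here; that depends on the source. The cost is protocol wording and one extra recorded field. No additional samples are needed.

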- Systolic BP <80 mmHg that a study investigator attributes to study drug-induced hypovolemia

- Patient desires not to continue furosemide
- Patient-reported symptom of severe or very severe
 - Rash
 - Tinnitus
 - Other self-reported symptom plausibly attributed to furosemide
 - Hearing change (also evaluated with the Inner Effectiveness of Auditory Rehabilitation (Inner EAR) instrument*)

*In addition to self-reported hearing change, we will monitor hearing with the Inner EAR instrument. The Inner EAR instrument measures hearing-related function and has good intra-rater reliability, internal consistency, discriminant validity, and responsiveness to change. Instrument scores correlate with pure tone audiometry.³⁸⁻⁴⁰ Scores range from 0 to 100 points. We will refer participants with ≥10-point decline in Inner EAR scores or self-reported hearing loss (any severity) after furosemide initiation and/or dose titration for audiometry testing. Audiometry for all participants is impractical (i.e. expensive, additional clinic visits) and unnecessary given low risk of hearing complications at the proposed doses (maximum 320 mg/ day).³²⁻³⁴

See **Section 7** for additional safety information (e.g. monitoring, adverse events and serious adverse events).

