3.2 Allocation to Treatment Groups and Blinding

All participants will receive oral furosemide. Participants and investigators are unblinded.

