4.2 Screening/Baseline Visit procedures

Screening

The PI will communicate with potential participants to determine whether they fit the inclusion/exclusion criteria and would like to participate in the study. If patients are interested in participating, a signed HIPAA waiver will be obtained to allow the PI to review the individual's medical record and confirm eligibility status. The study baseline period will begin within 2 weeks of enrollment.

Baseline

Written informed consent will be obtained from study participants prior to the implementation of any study procedures. The participant will receive a signed and dated informed consent form. See *Section 10.3.2* for details of consent process. The PI will verify inclusion/ exclusion criteria. A pregnancy inquiry will occur and a complete medical history will be obtained in weeks -4 to -2 of the baseline period. In the one week prior to start (week -1), the following data will be obtained: serum electrolytes, 24-hour urine collection, symptom assessment, and hearing assessment.

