4.4 Follow- up procedures (by visit types)

All study visits will occur at the time of routinely scheduled HD treatments at the patient's usual outpatient dialysis clinic. *Section 5* describes the measurements and assessments in detail.

Blood samples (weeks 1, 2, 3, 4, 5, 6, 10, 14, and 18): Blood will be obtained for the measurement of serum sodium, potassium, chloride, urea, creatinine, magnesium, calcium, albumin, and furosemide level. An additional 2.5 mL blood sample will be drawn, frozen, and stored in UNC Kidney Center -80° freezers for future testing as needed.

Urine samples (weeks -1, 5, 12, and 18): 24-hour urine collections will be obtained for the measurement of urine volume, sodium, urea, creatinine, and furosemide level. An aliquot of urine will be taken from the sample after the before-listed measurements are performed and be frozen and stored in UNC Kidney Center -80° freezers for future testing as needed.

Adherence assessments (weeks 1, 2, 3, 4, 5, 6, 8, 10, 12, 14, 16, and 18): Study staff will complete pill counts.

Acceptance assessments (weeks 1, 2, 3, 4, 5, 6, 8, 10, 12, 14, 16, and 18): Study staff will ask the participant the acceptance question.

Symptom assessments (weeks 1, 2, 3, 4, 5, 6, 8, 10, 12, 14, 16, and 18): Study staff will administer surveys evaluating patient-reported cramping, dizziness/pre-syncope, unusual tiredness/weakness, chest pain, rash, nausea, vomiting, diarrhea, tinnitus, hearing change, and numbness/tingling.

Hearing assessments (weeks 2, 4, 6, 10, 14, and 18): Study staff will administer the Inner EAR instrument.

Clinical data (weeks -4 to 18): HD treatment-level data (BPs, weights, dialysis prescription) will be obtained from the EHR.

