6.3.4 Primary analyses (each assessed separately)

At designated study time-points, we will determine the [data type; see **Section 6.1** for definitions]:

- change from baseline for the short and longer-term efficacy measure [binary] (24-hour urine volume);
- value of short and longer-term safety electrolyte measures [binary] (serum potassium, magnesium, corrected calcium);

- value of serum furosemide levels [binary] (short and longer-term safety furosemide level measure);
- incidence of dialysis-associated hypotension [binary] (short and longer-term safety blood pressure);
- incidence of severe or very severe patient-reported allergic or toxicity-related symptoms [binary] (short and longer-term safety symptom measures);
- change from baseline of Inner EAR instrument score [binary] (short and longer-term safety symptom measure);
- incidence of severe or very severe patient reported symptoms [binary] (short and longer-term tolerability symptom measures);
- incidence of patient-reported acceptance of furosemide [binary] (short and longer-term acceptability measure);
- incidence of adherence by pill counts [binary] (short and longer-term adherence measure).

Change measures and value measures (e.g. 24-hour urine volume, serum electrolytes, serum furosemide level) will be analyzed via one-way repeated measures of analysis of variance to determine the presence of absence of dose-related differences. In addition, we will use mixed effects modeling to test the effect of increased dose and duration with the fixed effect of time (dose), random subject effect, and an unstructured repeated covariance type. We will use generalized estimating equations to assess categorical outcomes (e.g. sufficient increase in 24-h urine volume, hypokalemia, hypomagnesemia, hypotension, symptoms, Inner EAR score, patient acceptance). We will also consider binary outcomes as rates (events/time).

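### The primary symptom endpoints depend on an unblinded attribution judgement with no named assessor or criteria, and the week -1 symptom scores are not used as a reference

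*Combined protocol and SAP*

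**What the plan says.** Section 6.1 defines the tolerability endpoint as the incidence of severe or very severe cramping, dizziness or pre-syncope, unusual "tiredness/weakness, chest pain, nausea, vomiting, or diarrhea not attributable to causes other than furosemide". The symptom safety endpoint has the same condition: "Incidence of severe or very severe patient-reported rash, tinnitus, or hearing change) not attributable to causes" other than furosemide. Section 2.1 and the synopsis repeat both, so the wording is deliberate.

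Two other safety endpoints in section 6.1 are built differently. Serious hypotension lists the kinds of cause that rule an event out (sepsis, myocardial infarction, other cardiovascular events). The hearing-scale endpoint, "Incidence of 10-point decrease in Inner EAR instrument score", has no attribution condition.

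On blinding, section 3.2 says: "Participants and investigators are unblinded". There is no control group.

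Section 4.2 collects at week -1: "serum electrolytes, 24-hour urine collection, symptom assessment, and hearing assessment". Follow-up is given in section 4.4: "Symptom assessments (weeks 1, 2, 3, 4, 5, 6, 8, 10, 12, 14, 16, and 18". That is six assessments in period 1 and six in period 2. Section 6.3.4 analyses hearing as "change from baseline of Inner EAR instrument score [binary] (short and longer-term safety symptom measure", but symptoms as plain incidence with no baseline term. Section 6.2 offers alternative definitions for efficacy, electrolytes, blood pressure, acceptability and adherence, but none for symptoms.

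Among the events that end up-titration, section 1.3.1 lists "Other self-reported symptom plausibly attributed to furosemide" at severe or very severe grade.

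**The concern.** Tolerability and symptom safety are primary aims, and section 7.5 calls safety and tolerability the main focus of the pilot. The condition means that the endpoint measures symptoms plus a judgement about their cause. Nothing says who makes that judgement, when, by what criteria, or how doubtful cases are classified. Any investigator making it would know that every participant is on furosemide, and no control arm exists to show how far the judgement is off.

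Appendix 13.1 sharpens the problem, because its question is framed around dialysis treatments. For cramping, dizziness, tiredness and nausea, dialysis is an alternative explanation that is always at hand. Two careful assessors could read the same forms and report quite different incidences.

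Section 6.4 says the pilot is to supply data on tolerability and safety and a basis for sizing a randomized trial. An incidence that cannot be separated from undocumented attribution is weak input for that.

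**Working it through.** **The plan's own figure.** The only power basis is in section 6.4 and concerns urine volume: 36 participants, mean change 5 mL/24-h, SD 10, two-sided 0.05, 83% power. A one-sample t-test with noncentrality 5/10 × √36 = 3.0 gives 83.1%, so it reproduces. It has no bearing on symptoms. No rate, precision or power is given for any symptom endpoint, so the rates below are assumptions.

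**Step 1: all-cause incidence over one period.** Section 6 measures short-term endpoints in period 1 and longer-term endpoints in period 2, so six assessments apply to each. With per-assessment probability p and independent visits, the chance of at least one event is 1 − (1 − p)^6.

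| p | At least one event in 6 |
|---|---|
| 3% | 1 − 0.97^6 = 17% |
| 5% | 1 − 0.95^6 = 26% |
| 10% | 1 − 0.90^6 = 47% |

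Symptoms that recur in the same people would lower these figures.

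**Step 2: effect of the attribution condition.** Let s be the share of participants with an event who are not counted because their events are attributed elsewhere. Counted incidence = all-cause incidence × (1 − s). Take an assumed all-cause incidence of 30% in 36 participants.

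| s | Counted incidence | Expected count of 36 |
|---|---|---|
| 0 | 30% | 10.8 |
| 50% | 15% | 5.4 |
| 90% | 3% | 1.1 |
| 95% | 1.5% | 0.5 |
| 100% | 0% | 0 |

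At s = 95% the chance of reporting no event at all is (1 − 0.015)^36 = 58%. A reported 0/36 has an exact 95% interval of 0 to 9.7%. An unfiltered 11/36 (31%) has an interval of 16% to 48%. The two intervals do not overlap, although the underlying symptom reports could be the same.

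**Step 3: would an any-worsening rule solve it?** Suppose an event were any severe score at some visit in a participant without one at week -1. With no drug effect and independent visits, the expected incidence is (1 − p) × [1 − (1 − p)^6]. At p = 5% this is 0.95 × 0.265 = 25%, and at p = 10% it is 0.90 × 0.469 = 42%. Six chances against one baseline produce apparent events without any drug effect. A per-assessment proportion avoids this, because one visit is compared with one visit.

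**Step 4: how good is the week -1 reference?** With 36 participants and p of 3-10%, between 36 × 0.03 = 1.1 and 36 × 0.10 = 3.6 participants would be expected to report a severe symptom at week -1. Sections 1.2, 3.5.2 and 4.3 admit people already taking furosemide or another loop diuretic, so their week -1 score is not drug-free. Appendix 13.1 uses one-week recall in titration and two-week recall in follow-up, and states none for baseline.

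**Step 5: attribution wording across sections.** The bullet quoted from section 1.3.1 asks whether furosemide is a plausible cause. Section 6.1 asks whether the symptom is attributable to something else. Severe dizziness could meet the first test and fail to count under the second, so up-titration could end for a symptom that the tolerability endpoint does not record. The fuller titration rules in sections 1.2, 3.5.2 and 4.3 name only rash, tinnitus and hearing change as symptoms, so the titration sections also differ among themselves.

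**The case against.** The best defence is that an all-cause count in a single-arm dialysis study is not a clean measure of tolerability either. On the assumed rates, 17-47% of participants would show a severe symptom in a period with no drug effect, and an attribution step is a reasonable attempt to remove that background. This stands. It is why the all-cause figure should sit beside the attributed one and be read against week -1, not replace it.

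The plan also keeps some unfiltered information. Adverse events are all-cause (7.1.1) and sought at every contact (7.3). Severe rash and tinnitus are reportable without attribution (7.3.2). The hearing scale has no filter and uses baseline, and acceptability and withdrawal are unfiltered. The rash and hearing-change items already imply change. This narrows the loss but does not repair the primary endpoint: the tolerability symptoms are not among the adverse events of interest in 7.3.1, and section 6.3.7 mentions changed outcome definitions only in general terms.

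A reader might go further and infer that the filter will remove nearly all events, or that the result is biased towards good tolerability. The documents support neither. An available alternative cause is not the same as an event attributed to it, undetermined events may still count, and near-total removal needs a share of about 90% or more. Nor do the documents say that study staff make the judgement; they are silent on who does.

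**Conclusion.** The point holds as a gap in endpoint definition. The primary symptom incidences can depend heavily on an unblinded judgement without a named assessor or criteria, and the week -1 scores that would give context are collected but not used in the symptom analysis. The exposure is greatest for cramping, dizziness, tiredness and nausea, and smaller for rash, tinnitus and hearing change.

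The size is illustrative only. With assumed background rates of 3-10% per assessment and independent visits, all-cause incidence over a period would be 17-47%, and the counted figure could fall anywhere between that and 0%. The actual size and direction cannot be derived from the documents. Pooling all 12 follow-up assessments would give larger figures, but no endpoint spans both periods. Nor should week -1 be treated as an objective, drug-free baseline: it is self-reported, and some participants are already on a loop diuretic.

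**What to change.** 1. In sections 6.1 and 6.3.4, add all-cause severe or very severe symptoms (score 3-4) as a proportion of assessments, by item and period, beside the week -1 proportion. One way is to include the week -1 visit in the generalized estimating equations already planned. Give this equal standing with the attributed endpoint.
2. Do not define an event as any visit worse than week -1, for the reason in step 3 of the working.
3. Show participants on a loop diuretic at entry separately. State the recall window used at week -1, and note that follow-up recall is two weeks against one in titration.
4. Keep the attributed endpoint, with a named assessor, written criteria, and a rule for doubtful cases.
5. Reconcile the attribution wording in section 6.1 (and 2.1 and the synopsis) with the bullet in section 1.3.1 and the titration wording in sections 1.2, 3.5.2 and 4.3.

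The cost is wording, a short attribution procedure and some added tables; all scores are already collected. The drawbacks are that the all-cause incidence will be higher and will include background dialysis symptoms, and that the reference is a single assessment resting on few events.
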